GEE	GENERALIZED ESTIMATING EQUATION
GGT	GAMMA GLUTAMYL TRANSPEPTIDASE
GSK3B	GLYCOGEN SYNTHASE KINASE 3 BETA
HGA1C	HEMOGLOBIN A1C
HC	HOMOCYSTEINE
HCT	HEMATOCRIT
HCY	HOMOCYSTEINE
HEENT	HEAD EARS EYES NOSE THROAT
HGB	HEMOGLOBIN
HIPAA	HEALTH INSURANCE PORTABILITY AND ACCOUNTABILITY ACT
HOMA-IR	HOMEOSTATIS MODEL ASSESSMENT OF INSULIN RESISTANCE
ICF	INFORMED CONSENT FORM
ICH	INTERNATIONAL CONFERENCE ON HARMONISATION
IDE	INSULIN DEGRADING ENZYME
IGF-1	INSULIN-LIKE GROWTH FACTOR-1
INI	INTRANASAL INSULIN
IRB	INSTITUTIONAL REVIEW BOARD
ITT	INTENT-TO-TREAT
LDH	LACTATE DEHYDROGENASE
LP	LUMBAR PUNCTURE
LTP	LONG TERM POTENTIATION
MCV	MEAN CORPUSCULAR VOLUME
ML	MILLILITER
MMA	METHYLMALONIC ACID
MMSE	MINI MENTAL STATE EXAMINATION
MPRAGE	MAGNETIZATION PREPARED RAPID GRADIENT ECHO
MR/MRI	MAGNETIC RESONANCE / MAGNETIC RESONANCE IMAGING
NBAC	NATIONAL BIOETHICS ADVISORY COMMISSION

NIA	NATIONAL INSTITUTE ON AGING
NIH	NATIONAL INSTITUTES OF HEALTH
NINCDS/ADRDA	NATIONAL INSTITUTE OF NEUROLOGICAL AND COMMUNICATIVE DISEASES AND STROKE / ALZHEIMER'S DISEASE AND RELATED DISORDERS ASSOCIATION
NBDA	N-METHYL – D-ASPARTATE
NSAID	NON-STEROIDAL ANTI-INFLAMMATORY DRUGS
OHRP	OFFICE FOR HUMAN RESEARCH PROTECTIONS
PBMC	PERIPHERAL BLOOD MONONUCLEAR CELL
PD	PROJECT DIRECTOR
PCP	PRIMARY CARE PHYSICIAN
PET	POSITRON EMISSION TOMOGRAPHY
PHI	PROTECTED HEALTH INFORMATION
PI	PRINCIPAL INVESTIGATOR
PID	PARTICIPANT ID
RBC	RED BLOOD CELL
RE	RANDOM EFFECTS
ROI	REGIONS OF INTEREST
SAE	SEVERE ADVERSE EVENT
SD	STANDARD DEVIATION
SGOT	SERUM GLUTAMIC OXALOACETIC TRANSAMINASE
SGPT	SERUM GLUTAMIC PYRUVIC TRANSAMINASE
T	TESLA
TSH	THYROID STIMULATING HORMONE
U/A	URINALYSIS
WBC	WHITE BLOOD COUNT

TITLE	Device Study for Intranasal Delivery of Insulin
PROJECT DIRECTOR	[name].
STUDY SPONSOR	Wake Forest University Health Sciences
STUDY PHASE	Phase II
INDICATION	Preclinical AD, Amnestic mild cognitive impairment (aMCI) or mild Alzheimer's disease (AD)
AIM OF STUDY	To determine the ability of an intranasal delivery device (Kurve ViaNase device) to increase levels of insulin in cerebrospinal fluid (CSF)
PRIMARY OBJECTIVE	To test the hypothesis that CSF insulin levels will increase 30 minutes after receiving a 20 International Units dose of insulin delivered with either the ViaNase device, compared to levels achieved 30 minutes after placebo.
SECONDARY OBJECTIVES	
 1. To test the hypothesis that memory performance measured with a list learning test (Auditory Verbal Learning Test) will be enhanced after insulin administration relative to placebo 2. To test the hypothesis that the CSF Aβ42/40 and the CSF Aβ/tau ratios will increase after insulin administration relative to placebo
PRIMARY OUTCOME MEASURE	CSF insulin
SECONDARY OUTCOME MEASURES	Memory test, CSF insulin, A β 40, A β 42, total tau, and phospho-tau 181
STUDY DESIGN	Single-site, double-blind, placebo-controlled study
SAMPLE SIZE	
 • n=30
SUMMARY OF KEY ELIGIBILITY CRITERIA	
 • Cognitively normal or • Diagnosis of aMCI (Petersen criteria) • Age: 55 to 85 yrs (inclusive)
DRUG DOSAGE & FORMULATION	20 International Units Humulin [®] R U-100 or matching placebo (saline)
DURATION OF PARTICIPATION	The approximate timeline for this 21 month study is projected as: 1) approximately 1 months for study startup activities including IND submission and IRB approval, and training; 2) approximately 18 months for data collection; 3) 2 months for assay and data analysis
PLACEBO	A matching placebo (sterile saline) will be used
ROUTE OF ADMINISTRATION	Intranasal
PROCEDURES	Physical and neurological exam, nasal examination, lumbar puncture, Vitals, Clinical Labs, CSF and blood analysis & banking and genotyping.

1.0 INTRODUCTION

An urgent need exists to find effective treatments for AD that can arrest or reverse the disease at its earliest stages. The emotional and financial burden of AD to patients, family members, and society is enormous, and is predicted to grow exponentially as the median population age increases. Current FDA-approved therapies are modestly effective at best. This study will provide information to assist in examining a novel therapeutic approach using intranasally administered insulin (INI) that has shown promise in short-term clinical trials. In a recent longer term trial in which INI was delivered with two devices (Kurve ViaNase device and Impel Precision Olfactory Delivery (POD) device, a different pattern of results was observed between the two devices, suggesting that differences in delivery systems can impact the therapeutic effects of insulin. The proposed proof of concept study will examine whether the device that was associated with clinical improvement is able to increase CSF insulin levels 30 minutes after administration, a timepoint which has been shown to represent the greatest increase in CSF insulin in a previous study (Born et al. *Nature Neuroscience*, 2002 Jun;5(6):514-6). If successful, information gained from the study will inform the design of future Phase III trials of intranasal insulin.

1.1 Primary Aim

To test the hypothesis that CSF insulin levels will increase 30 minutes after receiving a 20 International Units dose of insulin delivered with the ViaNase or device, compared to levels achieved 30 minutes after placebo

1.1.1 Secondary Aim 1

1. To test the hypothesis that memory performance measured with a list learning test (Auditory Verbal Learning Test) will be enhanced after insulin administration relative to placebo

1.1.2 Secondary Aim 2

1. To test the hypothesis that the CSF A β 42/40 and the CSF A β 42/tau ratios will increase after insulin administration relative to placebo

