synaptotoxicity and LTP disruption (Gasparini, Gouras et al. 2001, De Felice, Vieira et al. 2009, Lee, Kuo et al. 2009). Interestingly, A β also regulates brain insulin signaling. Soluble A β binds to the insulin receptor and disrupts insulin signaling and LTP induction in mouse hippocampal slice preparations (Townsend, Mehta et al. 2007). These effects could be prevented by exposing tissue to insulin prior to A β exposure. Insulin pre-treatment also prevented synthetic soluble A β oligomers from downregulating plasma membrane insulin receptors and reducing dendritic spines in primary hippocampal neurons (De Felice, Vieira et al. 2009). Insulin may also modulate A β degradation by regulating expression of insulin degrading enzyme (IDE), a metalloprotease that catabolizes insulin (Zhao, Teter et al. 2004). Collectively, these findings suggest that soluble A β may induce central nervous system (CNS) insulin resistance and synapse loss, and that treatment with insulin may prevent these pathological processes.

A role for insulin has also been suggested for other AD-related mechanisms. Insulin inhibits phosphorylation of tau, through its regulation of glycogen synthase kinase 3 β , a downstream target in the insulin signaling pathway (Hong and Lee 1997). Insulin dysregulation is also associated with oxidative stress, inflammation, and impaired neurogenesis (Craft and Watson 2004). Thus, insulin has been implicated in numerous processes related to AD pathophysiology, suggesting that correction of insulin dysregulation may be a therapeutic strategy with considerable clinical and scientific significance.

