4.4 Rationale for Biofluids

The CSF biomarkers insulin, A β 42, A β 40 and total tau will be measured. Plasma biomarkers including A β 42, and A β 40 will be also assessed. Plasma and CSF samples obtained in this study will be banked so that other putative biomarkers may be measured by qualified investigators in the future given adequate rationale and feasibility.

Several previous studies suggest that response to insulin may differ according to APOE genotype. In dose response studies that acutely elevated insulin through intravenous or intranasal administration, the greatest cognitive benefit was observed for adults with AD who were not ϵ 4 carriers (Reger, Watson et al. 2008). The current study will examine ϵ 4 carriage as a treatment response predictor.

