7.2 Baseline (Visit 2)

Results from all screening procedures must be reviewed and all inclusion/exclusion criteria must be met prior to proceeding to baseline. For participants whose screening visit was waived because they had received ADRC evaluations within the past 12-months will sign an informed consent form and HIPAA Authorization prior to administration of any study-related procedures.

According to the randomization schedule, the participant will receive a dose of 20 International Units insulin or placebo administered with the ViaNase device. They will then begin preparations for the lumbar puncture. After preparation, the immediate recall section of the AVLT will be administered. Blood for plasma biomarkers will then be collected immediately before and after participants undergo the lumbar puncture. Fasting plasma insulin, glucose, A β 40 and A β 42 will be measured. Additional plasma and serum will be collected and banked.

Lumbar puncture will then be performed in the morning after a minimum 8-hour overnight fast. CSF samples will be used to measure levels of insulin, A β 42, A β 40, total tau, and phospho-tau181. Additionally, CSF sample will be banked for future exploratory analysis. CSF will be collected and immediately frozen upright on dry ice. Site staff will call the participant within 24 hours from the lumbar puncture procedure to inquire about the participant's well-being and possible adverse events. Following the lumbar puncture, the delayed recall section of the AVLT will be administered. Participants will then receive a snack and instructions about post-lumbar puncture care.

7.3 Visit 3

Visit 3 will be scheduled within 2 to 6 weeks following Visit 1. Vital signs and weight will be obtained, a nasal examination will be conducted, adverse events and concurrent medications will be recorded. Procedures will follow the schedule outlined for Visit 1, except that the alternate compound (either saline or 20 International Units insulin) will be administered.

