10.0 BIOMARKER STUDIES

10.1 CSF

All CSF samples will be collected in the morning before breakfast and after an overnight fast. Participants who are taking anticoagulants, warfarin (Coumadin) and dabigatran (Pradaxa) should not be screened for this trial, as these are prohibited medications. Based on clinician judgment and depending on the clinical indication, it may be suitable to discontinue participants from their anti-platelet agent (e.g., aspirin, Plavix, NSAIDs) for 5-7 days prior to lumbar puncture and until at least 24 hours after lumbar puncture. It is not required that participants be discontinued from their anti-platelet agent in order to screen and enroll in the study.

A minimal total volume of CSF (25 ml) will be required for this study. To clear any blood from minor trauma associated with needle insertion, the first 1-2 mL of CSF are discarded (or more if needed). Collected CSF is aliquoted into sterile microtubes. Approximately 2ml of CSF or volume per local laboratory requirements will be sent at ambient temperature to the CRU laboratory for protein, glucose and cell count. The remaining CSF will be immediately frozen upright on dry ice for at least 20 minutes then stored at -70 until analysis.

CSF samples will be used to measure levels of insulin, A β 42, A β 40, total tau, and phospho-tau181. Assays will be performed by the Wake Forest ADRC Biomarker Service. CSF samples will also be frozen and stored for future analysis of putative biomarkers.

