11.0 STATISTICAL PLAN

Statistical analyses will be conducted by the ADRC Biostatistics Core. To address the Primary Aim, CSF insulin values will be subjected to a repeated measures analysis of variance with treatment (saline vs. placebo) as the repeated measure, with age and baseline MMSE as covariates. Secondary analyses will examine the effect of diagnostic status (cognitively normal vs. MCI) and APOE genotype. Secondary analyses will also examine treatment-related differences for other CSF and plasma biomarkers, and for memory scores.

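### Does Secondary Aim 2 need changing because its CSF Aβ42/tau ratio does not say which tau is meant?

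*Combined protocol and SAP*

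**What the plan says.** Section 1.1.2 states the hypothesis that two CSF ratios, Aβ42/40 and Aβ "42/tau ratios will increase after insulin administration relative to placebo". The Synopsis version of the same objective reads "the CSF Aβ/tau ratios will increase after insulin administration relative to placebo", so there the numerator has also lost its 42.

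The tau species is stated wherever this study's assays are listed:

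- Synopsis, Secondary Outcome Measures: "total tau, and phospho-tau 181", as separate outcomes beside Aβ40 and Aβ42. No ratio is listed.
- Section 7.2: "total tau, and phospho-tau181. Additionally, CSF sample will be banked for future exploratory analysis".
- Section 10.1: "total tau, and phospho-tau181. Assays will be performed by the Wake Forest ADRC Biomarker Service".
- Section 4.4: Aβ42, Aβ "40 and total tau will be measured", along with CSF insulin. Phospho-tau is not mentioned.

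The background in section 2.1 says "Insulin inhibits phosphorylation of tau, through its regulation of glycogen synthase kinase" 3β. The analysis text in section 11.0 is generic: "Secondary analyses will also examine treatment-related differences for other CSF and plasma biomarkers, and for memory scores". Section 4.2 gives the secondary measures a supportive role, and section 11.1 says that no power calculation was made.

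**The concern.** A directional hypothesis has a denominator that two assayed analytes could fill, and no sentence chooses between them. The hints also point in different directions. Section 4.4 suggests total tau, while the one insulin-tau mechanism in section 2.1 concerns phosphorylation. Section 11.0 does not settle it, because it names no ratio, analyte or scale.

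Read that way, an analyst could compute both ratios after unblinding and report the more favourable one. A reader could not tell which had been planned. If insulin acted on tau phosphorylation alone, the two ratios could give opposite answers. At stake would be the tau part of the evidence that section 4.2 calls supportive of access to and efficacy in the CNS.

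**Working it through.** **Reading the sections together.** Section 3.0, section 3.6 and the Methods in section 4.0 all use Aβ42 with plain tau, as section 1.1.2 does. The missing 42 in the Synopsis is therefore a slip. Phospho-tau is labelled as such each time it appears as an assay (Synopsis, 7.2, 10.1), and section 4.4 names total tau only. Unqualified tau is most naturally total tau. Section 4.4 does not say that total tau is the only species measured, so its silence on phospho-tau181 is an incomplete list and does not contradict 7.2 or 10.1. Section 2.1 is background and defines no endpoint.

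**Inputs.** From the documents: 30 participants, each receiving both treatments (sections 5.0, 5.1). Assumed, because the documents give none of them:

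- a two-sided 5% level;
- paired t-tests on log differences with equal SDs for Aβ42, Aβ40, total tau and phospho-tau181;
- correlations of 0.3, 0.5, 0.7 or 0.9 within the Aβ pair and, varied separately, within the tau pair;
- correlations of 0, 0.25 or 0.5 across the pairs.

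That is 4 × 4 × 3 = 48 settings, with 60,000 simulated trials each. The plan states no figure of its own to reproduce.

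**No true effect.** For the two tau ratios alone, the chance that at least one is significant is 1 − 0.95² = 9.75% if they were independent, and about 6.5% at correlation 0.95. Because they share Aβ42, the correlation between them is (1 − 2x + r)/(2 − 2x), where r is the tau-pair correlation and x the cross-pair correlation. Over the grid this runs from 0.3/1 = 0.30 (r = 0.3, x = 0.5) to 1.9/2 = 0.95 (r = 0.9, x = 0).

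| Ratios tested | Any two-sided p<0.05 | Any significant increase |
|---|---|---|
| Aβ42/40 and Aβ42/total tau | 8.8-9.8% | 4.4-4.9% |
| The same plus Aβ42/phospho-tau181 | 10.5-13.6% | 5.3-6.9% |
| Added within a setting | 1.4-4.2 points | 0.7-2.1 points |

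The last column matches the aim, which predicts an increase.

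**Insulin lowers phospho-tau181 only.** Set the shift so that Aβ42/phospho-tau181 has 80% power (standardized paired effect 0.529). The total-tau ratio is then significant in about 5% of trials and the two ratios disagree in 77-80%. Most of that is built in: one test has 80% power and the other has no effect, so even independent tests disagree in 0.80 × 0.95 + 0.20 × 0.05 = 77%.

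The same shift can be tested on phospho-tau181 itself, which the Synopsis lists as an outcome. In units of its own SD the effect is 0.529 × √(2 − 2x):

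| Cross-pair correlation x | Effect | Trials with phospho-tau181 significant |
|---|---|---|
| 0 | 0.748 | about 98% |
| 0.25 | 0.648 | about 93% |
| 0.5 | 0.529 | about 80% |

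The effect would be seen through a listed outcome.

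**Insulin shifts Aβ42.** This is the numerator of every ratio in Aim 2, and most of the Alzheimer-related rationale in section 2.1 concerns Aβ. With the same size of shift placed on Aβ42, both tau ratios move together and they disagree in 7-27% of trials.

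**The case for a change.** The strongest case for acting is that total tau is an inference: no sentence says it. The protocol labels tau in its assay lists and drops the label only in the hypothesis. One added word would settle the matter at no cost, and it could not be settled credibly after unblinding. If only tau phosphorylation responded, the choice of ratio would usually decide whether that ratio was significant.

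The first part stands. The analyte is unnamed, and it is good practice for the analyst to record it before the data are opened. The consequence does not follow. Near-certain disagreement between the ratios requires an effect on phospho-tau181 and none on Aβ42, whereas Aim 2 also predicts a rise in Aβ42/40. Even in that case the phospho-tau181 outcome is listed and compared between treatments, so the finding would not be lost. Selective reporting of a ratio would also be easy to spot, since both tau analytes are listed outcomes.

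**Conclusion.** No change to the plan is called for. The unnamed tau is a detail that an analyst would fill with total tau from section 4.4, and carrying out the plan as written gives no wrong result. The missing 42 in the Synopsis and the missing phospho-tau181 in section 4.4 are clerical, and other sections resolve both.

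The cost of leaving the choice open is small: about 1.4 to 4.2 percentage points on the chance of any nominally significant ratio, or 0.7 to 2.1 points if only increases count. These ranges rest on the assumed 5% level, equal SDs and correlation grid, and show scale only. The extreme 77-80% disagreement depends on assuming an effect on phospho-tau181 alone, which the plan's own outcome list would pick up in about 80-98% of trials. The matter concerns a supportive secondary aim in a proof-of-concept study and does not reach the primary comparison of CSF insulin.

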2.0 BACKGROUND AND SIGNIFICANCE

2.1 Rationale for Insulin

The rationale for the study is derived from growing evidence that insulin carries out multiple functions in the brain, and that insulin dysregulation may contribute to AD pathogenesis (Craft and Watson 2004). Insulin receptors are densely localized in the hippocampus and in entorhinal, frontal, and other cortical areas; they are found primarily in synapses, where insulin signaling modulates synaptogenesis and synaptic remodeling (Chiu, Chen et al. 2008, Zhao and Townsend 2009). Insulin facilitates memory at optimal levels, possibly through synaptic effects and enhanced hippocampal glucose utilization (Grillo, Piroli et al. 2009).

The importance of insulin in normal brain function is underscored by evidence that insulin dysregulation contributes to the pathophysiology of AD, a disorder characterized in its earliest stages by synaptic loss and memory impairment. Hoyer and colleagues first identified a reduction in insulin receptors and signaling markers in the AD brain (Frolich, Blum-Degen et al. 1998). This initial finding has been confirmed and extended by other investigators, who have demonstrated reduced CSF insulin in patients with AD and MCI (Craft, Peskind et al. 1998, Gil-Bea, Solas et al. 2010), and reduced insulin and IGF-I messaging with increasing AD pathology and cholinergic deficit (Rivera, Goldin et al. 2005). Insulin has a close relationship with β -amyloid, the toxic peptide produced by cleavage of the amyloid precursor protein (Zhao and Townsend 2009). In AD, insoluble A β peptides deposit in brain parenchyma and vasculature. Soluble A β species, particularly oligomers of the 42 amino acid species (A β 42), have synaptotoxic effects, possibly resulting in synapse loss, which is the earliest structural defect observed in AD (Selkoe 2008). Insulin reduces oligomer formation and protects against A β -induced

synaptotoxicity and LTP disruption (Gasparini, Gouras et al. 2001, De Felice, Vieira et al. 2009, Lee, Kuo et al. 2009). Interestingly, A β also regulates brain insulin signaling. Soluble A β binds to the insulin receptor and disrupts insulin signaling and LTP induction in mouse hippocampal slice preparations (Townsend, Mehta et al. 2007). These effects could be prevented by exposing tissue to insulin prior to A β exposure. Insulin pre-treatment also prevented synthetic soluble A β oligomers from downregulating plasma membrane insulin receptors and reducing dendritic spines in primary hippocampal neurons (De Felice, Vieira et al. 2009). Insulin may also modulate A β degradation by regulating expression of insulin degrading enzyme (IDE), a metalloprotease that catabolizes insulin (Zhao, Teter et al. 2004). Collectively, these findings suggest that soluble A β may induce central nervous system (CNS) insulin resistance and synapse loss, and that treatment with insulin may prevent these pathological processes.

A role for insulin has also been suggested for other AD-related mechanisms. Insulin inhibits phosphorylation of tau, through its regulation of glycogen synthase kinase 3 β , a downstream target in the insulin signaling pathway (Hong and Lee 1997). Insulin dysregulation is also associated with oxidative stress, inflammation, and impaired neurogenesis (Craft and Watson 2004). Thus, insulin has been implicated in numerous processes related to AD pathophysiology, suggesting that correction of insulin dysregulation may be a therapeutic strategy with considerable clinical and scientific significance.

2.2 Insulin as a Therapeutic Agent

The study uses insulin as a therapeutic agent and intranasal administration focusing on nose to brain transport as a mode of delivery. As reviewed above, insulin has pleiotropic effects on pathways implicated in AD pathogenesis. As such, augmenting CNS insulin is an alternative approach to AD therapy, in contrast to the majority of therapeutic approaches that focus on narrowly defined mechanisms such as acetylcholine modulation or amyloid accumulation. Restoring normal brain insulin levels in persons with AD may improve cognition and AD pathologic processes. Such an approach is possible with an intranasal administration technique.

2.2.1 Intranasal Pathways to the CNS

Olfactory sensory neurons are directly exposed to the external environment in the upper nasal cavity while their axons extend through the cribriform plate to the olfactory bulb. Following intranasal administration, drugs can be directly transported to the CNS, bypassing the periphery. Several extraneuronal and intraneuronal pathways from the nasal cavity to the CNS are possible. The extraneuronal pathways appear to rely on bulk flow transport through perineural channels to the brain or CSF. In recent studies, labeled INI or a closely related peptide, insulin-like growth factor-I (IGF-I), were administered to rodents (Thorne, Pronk et al. 2004, Francis, Martinez et al. 2008). Within 30 minutes, signal was detected along olfactory and trigeminal channels, as well as in the hippocampus, amygdala and rostral and caudal cortex. An additional extracellular pathway was identified with quick access to the CSF after absorption into the submucosa along the olfactory nerve and cribriform plate (Born, Lange et al. 2002, Frey 2002, Thorne, Pronk et al. 2004). These extracellular pathways provide direct access to the CNS within minutes of intranasal administration. Additionally, an intraneuronal pathway delivers drugs to the CNS hours or days later (Broadwell and Balin 1985, Shipley 1985, Baker and Spencer 1986, Balin, Broadwell et al. 1986). Viruses and microorganisms (Fairbrother and Hurst 1930, Faber 1938, Bodian and Howe 1941), amino acids (Weiss and Holland 1967), and proteins (Kristensson and Olsson 1971, Shipley 1985, Thorne, Emory et al. 1995) can also enter the CNS via nasal routes. In particular, substances with lower molecular weights are more likely to be transported to the CNS along intranasal pathways (Sakane, Akizuki et al. 1995). Insulin's molecular weight of about 5800 g/mol makes it a good candidate for intranasal delivery. Animal studies show labeled uptake to hippocampus and rostral and caudal cortex following INI administration (Francis, Martinez et al. 2008). In a murine diabetes model, INI reduced brain atrophy, while increasing synaptic markers and activation of Akt, CREB, and GSK3 β . Memory enhancement was also observed on Water Maze and radial arm tasks (Francis, Martinez et al. 2008). Human functional and cognitive studies of INI also support insulin's transport to the CNS. INI treatment increases CSF insulin levels and induces changes in auditory-evoked brain potentials compared to placebo (Kern, Born et al. 1999). INI improves verbal memory

07-December-2020

IND #: 119232

acutely in persons with AD and aMCI without affecting plasma insulin or glucose levels at the dose included in the study (Reger, Watson et al. 2006). Regarding chronic effects, several studies reported that 2 months of daily insulin administration (160 International Units/day) significantly improves verbal memory in young healthy adults (Benedict, Hallschmid et al. 2004, Stockhorst, de Fries et al. 2004, Benedict, Kern et al. 2008, Hallschmid, Benedict et al. 2008, Stockhorst, de Fries et al. Submitted for publication). Finally, Section 3.0 presents results in a preliminary study in which insulin was administered to adults with AD or aMCI for 4 months.

